We plan to study this phenomenon using seven different FDA-approved vaccines; by characterizing Fc glycans in pre- and post- immunization sera, we will define the type of antigen(s) that can elicit changes in Fc glycan composition in humans. We will also study whether healthy adults who have been previously infected with a flavivirus or alphavirus (dengue, zika or chikungunya) generate distinct Fc glycoforms after vaccination compared with healthy adults who have not had known infection with dengue, zika or chikungunya virus infection; for this study we will use the **seasonal inactivated influenza** vaccine because influenza reagents for analysis of the TIV-elicited IgGs are abundant and readily available.

We will also use existing serum samples from controlled influenza virus infection studies performed at the NIAID in order to study how specific Fc glycoforms on influenza-specific IgGs may change during infection and to compare Fc glycan modulations that may occur during infection with those elicited by vaccination. In addition, we will use existing serum samples from a study performed at Emory University. These samples were drawn from patients with dengue virus infection, during acute infection, following defervescence and 1-2 months post infection. We will use these samples to study how Fc glycoforms on dengue envelope protein-specific IgGs may change during infection and we will compare any changes with those observed on IgGs from patients with influenza virus infection.

That antigen exposure can modify Fc glycan composition suggests a possible role for cognate B cell - T cell interactions in the regulation of glycan composition. Accordingly, a second phase of this study will investigate whether T cell help is required for vaccine-elicited glycan modification. We will study this by comparing serum IgG Fc glycan profiles in volunteers who were vaccinated with either T cell dependent (TD) or T cell independent (TI) vaccine antigens. We will also evaluate whether the age of the patient or route of vaccine administration are determinants of vaccine-elicited glycan modification. Finally, we plan to study how specific IgG glycan modifications regulate immunity against *Streptococcus pneumoniae* and against influenza viruses in *in vitro* and *in vivo* models of infection.

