**Aim 1:**

To determine whether vaccination can elicit modifications in Fc glycan composition and, if so, whether the T cell dependence of a vaccine antigen, age of the patient at vaccination or route of vaccine exposure regulate observed modifications in the IgG Fc glycan.

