**The study will occur in four phases:**

**Phase 1:** Volunteers will be recruited to receive influenza vaccines (Groups 1, 2, 7, 10). Recruitment for Groups 1 and 7 will occur simultaneously and volunteers will be enrolled sequentially - enrollment into Group 1 will be given priority over Group 2 because the intradermal vaccine preparation for the 2012-13 influenza season will expire earlier than the intramuscular preparation (April 2013 vs. June 2013). Volunteers will be recruited to receive the Flumist influenza vaccine (Group 10) beginning fall of 2013.

**Phase 2:** Volunteers will be recruited to receive one of the pneumococcal vaccines (Groups 3, 4, 8, 9)

- these subjects will be recruited simultaneously and will be randomized to receive either the Pneumovax or Prevnar vaccines.

**Phase 3:** Volunteers will be recruited to receive one of the meningococcal vaccines (Groups 5 and 6) - these subjects will be recruited simultaneously and will be randomized to receive either the MPSV4 or Menveo vaccines.

**Phase 4:** Volunteers will be recruited for Arm III of the study to receive the Fluzone intramuscular vaccine (Groups 11-14)

Study participants will not be blinded. During the analysis phase, samples will be coded so that the precise vaccine administered within each phase is unknown.

Study visits will be scheduled as follows for groups 1-10: screening, day 0 (within 4 weeks of screen), day 7 safety visit, and weeks 3, 5, 7, 9, and 12. On Day 3-4, a telephone call will be made to check on subject's medical status.

Groups 11-14 will be scheduled as follows: day 0 (within 4 weeks of screen), day 7 safety visit, and week 3. We will not collect samples at weeks 5, 7, 9 or 12 for Groups 11-14 because our existing data on intramuscular Fluzone immunization from Group 2 demonstrate that the major Fc glycan modifications occur during the first 3 weeks following vaccination.

**We do not anticipate any safety issues related to this protocol as all vaccines to be used have been FDA approved and all study participants are healthy adults.**

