#### **12.10 \* Data Analysis**

Describe method(s) of data analysis.

In order to find evidence that IgG Fc glycan composition changes from pre- to post-vaccination, we will apply two-sided t-tests and wilcoxon

tests for paired samples with significance fixed at 5% when evaluating change in abundance of specific saccharide units. For each vaccine antigen, we will be comparing pre- (day 0) to post- (day 21) vaccination IgG Fc glycan composition in order to see which vaccines elicit significant saccharide modifications. We will apply the same analysis to data obtained through study of samples taken prior to and at day 21 post influenza virus infection. For the analysis of the time course experiment and comparison across different groups, we are going to use Repeated Measures ANOVA, descriptive graphics and possibly fitted curves that may bring information about changes in time. Depending upon results in humans (Aims 1 and 2), in vivo experiments will be carried out in mice. For this stage, our Biostatistical Core will be consulted about the appropriate design and analysis of the experiments.

**12.11 \* Explain the rationale for the choice of statistical measures and the number of participants proposed for the study, including the power calculations when applicable.**

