Sample size evaluation was carried out to provide 80% power and 5% of significance for a two-tailed paired t-test to verify pre-post differences in the relative abundance of sugars. For each one of the specific saccharides to be measured, we expect an effect size a 10% change in relative abundance, with a standard deviation of 4.4% - this is based on data presented in Selman et al. (2012). Selman et al. evaluated changes in IgG1 Fc saccharide abundances (galactosylation, fucosylation and sialylation) following influenza vaccination of 10 Caucasian adults. Based on their data, we selected the highest standard deviation, which occurred in abundance of sialylation. Adjustments for error multiplicity were done by a Bonferroni-Correction that reduced the individual significance levels to be 0.017 (0.05 significance divided by 3 sugars evaluated). Another adopted measure for taking into account the uncertainty about the standard deviation was to inflate that estimate by multiplying it by 1.30. This caused our standard deviation to increase to 5.72% from 4.4%. After all described procedures, using the function *n.ttest* in package *samplesize* in R, the initial evaluated sample size resulted in n=7 per group. It is important to emphasize that only samples from subjects with a two-fold increase in vaccine-specific antibody titer will be further analyzed for IgG Fc glycan saccharide composition. Thus, the evaluated sample size was increased to n=10 to accommodate the possibility of having a 20% rate of vaccine non-responsiveness and also the expected rate of volunteer drop-off (10%).

**ARM III:** We have preliminary data on the abundance of afucosylated glycans on anti-dengue envelope protein IgG

from patients with acute dengue virus infection- the data are from one time point (acute infection) and we are comparing two groups: patients with dengue hemorrhagic fever (the severe disease) vs. dengue fever (the mild form of the disease). The maximum coefficient of variation between the two groups was 55%. Assuming that for the present study the populations to be sampled will have the same variability, a sample size of n = 25 (per group) would guarantee 80% power at 5% significance to detect a minimum Fold-Change (FC) of 1.5 (50% increase) when comparing two independent groups with an unpaired two-sided t-test. In this calculation, we are taking into account that 5 pairwise comparisons will be performed, thus the test-wise significance level will be reduced to 0.01.

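### The T-cell-dependence question in Aim 1 has no specified between-vaccine contrast; a Day 0-adjusted Day 21 contrast stratified by the randomised vaccine pairs would answer it better from the same data

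*Combined protocol and SAP*

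**What the plan says.** Aim 1 (section 12.6) asks "whether the T cell dependence of a vaccine antigen, age of the patient at vaccination or route of vaccine exposure regulate observed modifications". The Overview (12.1) says the T-cell part will be studied by "comparing serum IgG Fc glycan profiles in volunteers who were vaccinated with either T cell dependent (TD) or T cell independent (TI) vaccine antigens".

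The design supports that comparison. Under the four phases in section 12.9, pneumococcal volunteers (Groups 3, 4, 8, 9) are randomised between Pneumovax and Prevnar. Meningococcal volunteers (Groups 5, 6) "will be randomized to receive either the MPSV4 or Menveo vaccines". The arm definitions identify each pair as plain polysaccharide against conjugate.

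Section 12.10 gives two tools:
- Within each vaccine, Day 0 is compared with Day 21 by two-sided t and Wilcoxon "tests for paired samples with significance fixed at 5% when evaluating change in abundance of specific saccharide units". The stated purpose is "in order to see which vaccines elicit significant saccharide modifications".
- Between groups: "For the analysis of the time course experiment and comparison across different groups, we are going to use Repeated Measures ANOVA", followed by descriptive graphics and possibly fitted curves. Factors, groups, visits and contrast are not given.

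Section 12.11 sizes only the within-vaccine test: "Sample size evaluation was carried out to provide 80% power and 5% of significance for a two-tailed paired t-test". It sets a Bonferroni level of 0.05/3 = 0.017 per sugar, although 12.10 says 5%. For Arm III the same section does name a between-group test, the number of comparisons and the test-wise level. Nothing equivalent is given for TD versus TI.

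**The concern.** Whether T-cell dependence regulates the change is a question about the difference between two changes. The only fully specified test for Aim 1 looks at each change alone. A significant change after one vaccine and a non-significant change after its partner is not evidence that they differ.

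The between-group tool is named but left open. It could be run as a six-group omnibus test, pair by pair, or with a pooled two-level TD/TI factor, and these differ widely in power. It could use two visits, three, or all seven sampling visits. None of these versions, as written, adjusts for Day 0 or uses the fact that the same TD-TI comparison is randomised in three pairs. If the pairs are analysed separately, each has about 7 against 7, a number chosen for a different question. Analysts could also choose among the versions after seeing the data.

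**Working it through.** **Inputs from section 12.11.** Within-group change 10 points; SD 4.4 x 1.30 = 5.72; 80% power; two-sided alpha 0.05/3; 7 evaluable per group; 10 enrolled, allowing 20% non-response and 10% drop-out.

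**Assumptions (not in the documents).** TD-TI difference in change d = 5 points, with 10 also shown; Day 0 to Day 21 correlation r = 0.3 to 0.7; 5.72 is the SD of change; 7 evaluable in each of six groups.

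**1. The plan's own figure.** Paired t-test by noncentral t, non-centrality 10 x sqrt(n)/5.72, alpha 0.05/3: n = 6 gives 73.8% and n = 7 gives 85.9%. So n = 7 reproduces. Inflation: 7/(0.8 x 0.9) = 9.7, or 7/0.7 = 10, so n = 10 reproduces.

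**2. TD-TI contrast at d = 5.** Non-centrality is d/(s x sqrt(2/N)), with N per vaccine type. On change scores s = 5.72. With Day 0 adjustment s = 5.72 x sqrt((1 + r)/2), giving 4.61, 4.95 and 5.27 for r = 0.3, 0.5 and 0.7. Pooled degrees of freedom allow for six cell means (42 - 6 = 36), less one for Day 0.

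| Analysis | N per type | df | Non-centrality | Power, alpha 0.05 | Power, alpha 0.017 |
|---|---|---|---|---|---|
| One pair, change | 7 | 12 | 1.64 | 32.5% | 17.2% |
| Three pairs, change | 21 | 36 | 2.83 | 78.7% | 62.8% |
| Three pairs, adjusted, r = 0.7 | 21 | 35 | 3.07 | 84.8% | 70.9% |
| Three pairs, adjusted, r = 0.5 | 21 | 35 | 3.27 | 88.9% | 77.1% |
| Three pairs, adjusted, r = 0.3 | 21 | 35 | 3.51 | 92.7% | 83.5% |

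At alpha 0.05 pooling multiplies power by 78.7/32.5 = 2.4. Day 0 adjustment at r = 0.5 adds a factor of 88.9/78.7 = 1.13.

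**3. At d = 10.** One pair has 85.1% (alpha 0.05) or 68.5% (0.017), and the pooled adjusted model about 100%. The ratios are 1.18 and 1.46. At r = 0.5 the pooled adjusted model more than doubles the power of one pair only for d of about 1.4 to 6.4 at alpha 0.05, or 1.1 to 8.25 at 0.017.

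**4. Against an ANOVA with a pooled TD/TI factor.** Type-by-time test by noncentral F under compound symmetry, error SD 5.72/sqrt(2), n = 21 per type, d = 5, with an illustrative time profile peaking at Day 21. At alpha 0.05 power is 79% with two visits, 70% with three and 62% with seven, against 88.9%: ratios 1.1 to 1.4. A six-group omnibus group-by-time test with three visits, by simulation, has about 37% against 88%.

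**5. If the pairs differ.** A 5-point effect in one pair only averages 5/3 = 1.67. At alpha 0.05 and r = 0.5 the pooled model then has 18.5%, against 40.7% for the adjusted test in that pair alone. For 10 points in one pair the figures are 56% and 93%.

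**6. Reading significance patterns.** With power P for each vaccine and equal true effects, a pair disagrees with probability 2P(1 - P). On the plan's inputs (10 points, n = 7), P = 0.859 at alpha 0.017 gives 24%; P = 0.968 at alpha 0.05 gives 6%. With both true changes at 5 points and alpha 0.05, P = 0.49 gives 50%.

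**The case against.** A reader might infer that the plan judges T-cell dependence by which vaccines reach significance. The documents do not support that. Section 12.10 assigns the paired tests to detecting change from pre- to post-vaccination, which is the first half of Aim 1, and gives between-group comparison to the ANOVA. Step 6 therefore shows only why such a reading should be ruled out.

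A reader might also infer that the proposed model doubles power in general, or that the TD-TI question is close to unanswerable as designed. Neither follows. Section 12.10 does not forbid a pooled TD/TI factor, and against that the gain is modest. At 10 points, the only effect size the plan gives, one pair already has 85% at alpha 0.05.

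Nor is pooling free. Aim 1 itself treats age as a possible modifier, and step 5 shows the loss if effects differ between pairs. Section 12.11 also restricts glycan analysis to participants with a two-fold titre rise. That selection follows randomisation and may act differently on plain and conjugate vaccines, so the contrast is not fully protected and 21 against 21 is itself an assumption.

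The SD is open to two readings: 12.11 does not say outright that 4.4% is the SD of change. If it describes abundance, pooled adjusted power at alpha 0.05 is 82-97%, rising with the correlation.

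Drop-out is a minor argument: the 7 per group already allows for it, and the plan does not say that all seven visits enter the ANOVA.

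These points limit the size of the gain. They leave the missing contrast in place, and the adjusted, stratified model had more power than every ANOVA form in step 4.

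**Conclusion.** The point holds in this form: the plan specifies no TD-TI contrast, and a stratified, Day 0-adjusted contrast is a better method available from the groups already enrolled. At a 5-point difference, power rises from about 33% (one pair, change scores) to 85-93% at alpha 0.05, or from 17% to 71-84% at 0.017. This rests on the assumed difference and correlation, 5.72 as the SD of change, 7 evaluable per group and a common effect across the three pairs. It is an improvement that should be made; the sample size for the within-vaccine question is sound as calculated.

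**What to change.** Amend section 12.10 as follows:

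- For each sugar, test TD versus TI in one linear model: Day 21 abundance on Day 0 abundance, vaccine type (TD or TI) and vaccine pair (Groups 3 v 4, 8 v 9, 5 v 6). Use two-sided alpha 0.017, removing the conflict with the 5% now stated.
- Report the estimate for each pair and the pair-by-type interaction beside the pooled estimate.
- For the time course, replace Repeated Measures ANOVA with a mixed model using all available visits.
- State that conclusions on T-cell dependence, age and route rest on direct contrasts, and not on which vaccines reach significance. No randomisation is described for age or route.
- Report the proportion reaching the two-fold titre rise by vaccine beside the TD-TI result.

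**Cost.** Wording and analyst time; no added participants or samples. The price is interpretive: the pooled estimate is an average over pathogen and age and loses power if the pairs differ. A sensitivity analysis that adds non-responders with measurable IgG would help with the responder restriction, but it would need extra assays.

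### Where 5% family-wise control is intended, Holm's step-down procedure would gain power over the single-step Bonferroni levels at no cost in error, and section 12.10 should name it

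*Combined protocol and SAP*

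**What the plan says.** The two relevant sections do not describe the same thing.

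- **Section 12.11, Arms I and II.** The calculation was made "to provide 80% power and 5% of significance for a two-tailed paired t-test". The allowance for multiplicity is stated as: "Adjustments for error multiplicity were done by a Bonferroni-Correction that reduced the individual significance levels to be 0.017", which is 0.05/3 for the three sugars. The result before allowing for losses is given as "the initial evaluated sample size resulted in n=7 per group".
- **Section 12.11, Arm III.** The sizing of 25 per group takes into account that "5 pairwise comparisons will be performed, thus the test-wise significance level will be reduced to 0.01". The word Bonferroni is not used here, but 0.05/5 = 0.01 is the same single-step division. The five comparisons are not listed.
- **Section 12.10, Data Analysis.** Paired t-tests and Wilcoxon tests are planned for each saccharide, with significance set at 5%. No multiplicity procedure is named, and neither 0.017 nor 0.01 appears.

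Section 12.7 lists galactosylation, fucosylation and sialylation together as primary readouts. Section 12.11 applies the same expected change to each of them.

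**The concern.** A single-step Bonferroni rule holds every test to the strictest level, however many of the other hypotheses have already been rejected. Holm relaxes the level after each rejection and keeps the same family-wise guarantee. The difference is largest when several effects are real, which is what section 12.11 assumes for the three sugars.

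The scientific question in Arm I is which sugars a vaccine changes, not only whether any sugar changes. With about seven evaluable people in a group of ten, a group's profile could be reported as partial because one real change fell between 0.017 and the level Holm would have allowed. Arm III is exposed in the same way, and starts from less power.

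**Working it through.** **Inputs, all from section 12.11.** Two-sided paired t-test; family-wise level 0.05; three sugars. For the effect, "we expect an effect size a 10% change in relative abundance, with a standard deviation of 4.4" per cent. After multiplying by 1.30, "This caused our standard deviation to increase to 5.72% from 4.4" per cent. For Arm III: coefficient of variation 55%, fold-change 1.5, n=25 per group, unpaired two-sided t-test, level 0.01.

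**Step 1. Reproduce the plan's n=7.**
Standardised effect d = 10/5.72 = 1.748. Level = 0.05/3 = 0.0167. At n=7 the noncentrality is 1.748 × √7 = 4.63 on 6 degrees of freedom and the critical value is 3.29. Exact power is 85.9%. At n=6 it is 73.8%. So n=7 reproduces. With 20% non-response and 10% drop-off, 7/(1 − 0.30) = 10 and 7/(0.8 × 0.9) = 9.7, so n=10 reproduces as well.

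**Step 2. Write out the two rules.**
Bonferroni compares every p-value with 0.05/3. Holm orders them and compares the smallest with 0.05/3, the next with 0.05/2 and the largest with 0.05, stopping at the first failure. The first step is identical, so the chance of at least one rejection is identical. Holm can differ only from the second step on.

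**Step 3. Simulate three paired t-tests at n=7, SD 5.72** (200,000 trials per setting). The documents give no correlation between sugars, so 0 and 0.5 are assumptions.

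| Sugars changing by 10 points | Measure | Bonferroni | Holm |
|---|---|---|---|
| All three | Power per sugar | 86% | 94-96% |
| All three | All three detected | 64-69% | 90% |
| All three | At least one detected | 98-99.7% | the same |
| Two | Power per changing sugar | 86% | 90-91% |
| One | Power for that sugar | 85.9% | 86.0-86.1% |
| None | Family-wise error | 5% or less | the same |

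At a correlation of 0.8 the all-three figures are 75% and 91%. At n=10, with nobody lost, power per sugar is already about 98.5% with Bonferroni, so the gain there is negligible.

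**Step 4. Arm III.** Assume the five comparisons are Groups 11 to 14 each against Group 2, plus Group 11 against Group 12. The 55% can be read in more than one way:
- Raw scale, SD = 0.55 of the reference mean: d = 0.5/0.55 = 0.909.
- Log scale, SD = √ln(1 + 0.55²) = 0.514: d = ln(1.5)/0.514 = 0.789.

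At two-sided 0.01 and n=25, exact power is 70% (raw) or 55% (log). The stated 80% does not reproduce; it needs 30 or 40 per group.

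If all four infection groups differ 1.5-fold from Group 2, Holm raises power per comparison from 70% to 77% (raw) or from 55% to 61% (log). If only one group differs, it reaches about 72% or 56%.

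**Step 5. Compare with unadjusted testing.** If section 12.10 means 5% for each test, power per sugar at n=7 is 96.8%, above Holm's 94-96%. Family-wise error with no true change would be about 13-14% (for independent sugars, 1 − 0.95³ = 14.3%).

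**The case against.** The strongest reply is that Bonferroni appears only in the sizing. Section 12.10, which governs the analysis, names no adjustment, so Holm would replace something the analysis section does not contain. If 5% per test is what is meant, Holm is stricter than the written plan (step 5). This stands as a limit: the point does not hold whichever way section 12.10 is settled. It holds where family-wise control is intended. Section 12.11 points that way, since its Arm III sentence speaks of the level at which the comparisons will be tested.

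Other replies also stand in part:

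- **Bonferroni is valid and the sizing target is met.** Power is 86% per sugar against 80%, and the SD is deliberately conservative: at the uninflated 4.4, Bonferroni power at n=7 is 98%. The plan powers each sugar; detecting all three is a stricter criterion that it does not set. A reader might infer a mistake in the plan. The documents do not support that.
- **The gain is conditional.** It is almost nil if only one sugar changes.
- **Seven evaluable people is not general.** Group 2 enrols 25, about 25 × 0.8 × 0.9 = 18 after the planned losses, and the NIAID infection samples come from about 30 people. Power there is already near 100% at the plan's inputs.
- **The five Arm III comparisons are a guess**, and the size of the gain depends on it.

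What does not stand is the suggestion that the choice is a matter of taste. Where 5% family-wise error is the aim, Holm never rejects less than Bonferroni and can reject more.

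**Conclusion.** The point holds as an improvement at no cost in error, where 5% family-wise control is intended. At the plan's own inputs and seven evaluable people, Holm raises power per sugar by about 8 to 10 percentage points and the chance of detecting the full three-sugar profile from 64-69% to 90%. This rests on all three sugars changing by 10 points and on assumed correlations of 0 to 0.5.

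A reader might infer that, with Holm, all the sample sizes can stay as they are. For the three-sugar tests that is so. For Arm III it is not shown: 77% or 61% still misses the 80% that section 12.11 claims for n=25. Holm passes 80% only on the raw scale with all five differences real, where the 1.5-fold comparisons reach 83-85%. That power statement needs separate restatement.

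**What to change.** In section 12.10, cross-referenced in 12.11, state that family-wise error is held at 5% by Holm's procedure:

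- **For each vaccine:** over the three sugar p-values, ordered and compared with 0.05/3, 0.05/2 and 0.05. All three come from one prespecified test: the paired t-test used for sizing, with the Wilcoxon test as a sensitivity analysis.
- **For Arm III:** over five comparisons listed by group number, compared with 0.05/5, 0.05/4, 0.05/3, 0.05/2 and 0.05.

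This also removes the mismatch between the 5% in section 12.10 and the reduced levels in 12.11. If unadjusted 5% testing is in fact intended, section 12.10 should say so and 12.11 should be made consistent with it.

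The cost is a sentence and a list, with no added participants, visits or assays. Simultaneous confidence intervals that match Holm decisions are less simple; Bonferroni intervals can be shown alongside. The change should be made before the remaining data are analysed.

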**215 volunteers who meet all the eligibility criteria will be enrolled in this study.**

The study is divided into 3 arms. The groups are defined as follows:

**Arm I: Age 18-64 group:** Groups of 10 study participants each (except for group 2 which includes 25 participants) < 65 years of age (< 50 years of age for Flumist vaccine and < 55 years of age for meningococcal vaccines) will be **vaccinated with one of seven FDA approved vaccines (85 participants total):** **Group 1)** Fluzone intradermal influenza virus vaccine, **Group 2)** Fluzone intramuscular influenza virus vaccine, **Group 3)** Pneumovax 23 (plain polysaccharide pneumococcal vaccine), **Group 4)** Prevnar/PCV13 (pneumococcal conjugate vaccine), **Group 5)** MPSV4 (plain polysaccharide meningococcal vaccine), **Group 6)** Mencevo (meningococcal conjugate vaccine), **Group 10)** Flumist Quadrivalent (intranasal influenza live vaccine).

**Arm II: Age 65-80 group:** Groups of 10 study participants ≥65 years of age will be **vaccinated with one of three of the FDA approved vaccines (30 participants total):** **Group 7)** Fluzone intramuscular influenza virus vaccine, **Group 8)** Pneumovax 23, **Group 9)** Prevnar. Meningococcal vaccines, the intradermal influenza vaccine and intranasal Flumist will not be administered to participants in Arm II.

**Arm III: Healthy adults, age 18-80, with a specific medical history as described here and in Section 12.11 (Inclusion Criteria):** Groups of 25 study participants will be vaccinated with the Fluzone intramuscular influenza virus vaccine (100 participants total). **Group 11)** Prior diagnosis of dengue fever or dengue virus infection. **Group 12)** Prior diagnosis of dengue hemorrhagic fever. **Group 13)** Prior diagnosis of chikungunya virus infection. **Group 14)** Prior diagnosis of zika virus infection

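### Arm III: on the plan's own inputs, 25 per group at a two-sided test-wise level of 0.01 gives at most about 70% power for a 1.5-fold change, not the stated 80%

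*Combined protocol and SAP*

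**What the plan says.** The ARM III paragraph of Section 12.11 is the only sample size justification for Groups 11 to 14, which hold 100 of the 215 planned participants (Section 12.9, Study Design) and serve Aim 4.

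- **Variability.** The pilot data are afucosylated glycans on anti-dengue envelope IgG in acute infection, severe against mild disease. "The maximum coefficient of variation between the two groups was 55" per cent. This is carried over: "Assuming that for the present study the populations to be sampled will have the same variability".
- **Claim.** "a sample size of n = 25 (per group) would guarantee 80% power at 5% significance to detect a minimum Fold-Change (FC) of 1.5".
- **Test.** The claim applies "when comparing two independent groups with an unpaired two-sided t-test".
- **Multiplicity.** The paragraph says that the calculation itself allows for five pairwise comparisons, "thus the test-wise significance level will be reduced to 0.01".

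The paragraph does not give the scale (raw or log), the formula or software, or any allowance for drop-out or vaccine non-response in Arm III.

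**The concern.** Every input except the scale is stated, so the 80% can be checked. A standardised difference of about 1.00 is needed for 80% power with 25 per group at a two-sided 0.01. A 50% increase against a CV of 55% gives at most 0.5 / 0.55 = 0.91, so the claim looks too favourable before any detailed work.

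The figure is the whole stated case for the size of Arm III, and it is worded as a guarantee. If it is wrong, anyone judging what Arm III can show about prior dengue, zika or chikungunya infection starts from a sensitivity that the design does not have on its own assumptions.

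**Working it through.** **Inputs (Section 12.11, ARM III).** n = 25 per group; fold-change 1.5; CV 0.55; two-sided unpaired t-test; test-wise level 0.05 / 5 = 0.01; target power 80%.

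**Method.** Power = P(|T| > t_crit), where T is noncentral t with 2 x 25 - 2 = 48 degrees of freedom and noncentrality d x sqrt(25/2) = 3.536 d. At a two-sided 0.01, t_crit = 2.682.

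**Converting the CV to d.** The scale is not stated, so three readings are shown, with the reference mean set to 1:

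- A, raw scale, common SD = 0.55 x reference mean: d = 0.5 / 0.55 = 0.909.
- B, log scale: sigma = sqrt(ln(1 + 0.55^2)) = sqrt(ln 1.3025) = 0.514; d = ln 1.5 / 0.514 = 0.789.
- C, raw scale, CV 55% in both groups: SDs 0.55 and 0.825; root mean square = sqrt((0.3025 + 0.6806) / 2) = 0.701; d = 0.5 / 0.701 = 0.713.

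**Results at a two-sided 0.01.**

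| Reading | d | Noncentrality | Power at n = 25 | n per group for 80% | Fold-change at 80%, n = 25 |
|---|---|---|---|---|---|
| A | 0.909 | 3.21 | 70.1% | 30 | 1.55 |
| B | 0.789 | 2.79 | 54.6% | 40 | 1.67 |
| C | 0.713 | 2.52 | 44.4% | 48 | 1.80 |

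The last column sets d = 1.00, the value that gives 80% power. A: 1 + 1.00 x 0.55 = 1.55. B: exp(1.00 x 0.514) = 1.67. C: the fold-change F that solves (F - 1) / (0.55 x sqrt((1 + F^2)/2)) = 1.00, which is 1.80.

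**Checks.** The normal approximation gives 73.8%, 58.4% and 47.8%, still below 80%. Simulation (100,000 runs) gives 54.7% for B and 44.5% for C.

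**Can the plan's figure be reproduced?** Not with the stated inputs. These departures come close:

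- One-sided 0.01, reading A: power 78.7%; n = 26 (25 by the normal approximation).
- Two-sided 0.05 with no adjustment for five comparisons, reading B: power 78.0%; n = 27 (26 by the normal approximation).
- One-sided 0.05, reading C: power 80.0%; n = 26 (25 by the normal approximation).

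With n = 25 and a two-sided 0.01 kept, 80% power would need a CV of about 50% (reading A) or 42% (reading B), not 55%.

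**The case against.** **The gap depends on an unstated scale.** This is fair. On reading A the shortfall is modest: 70% against 80%, 30 per group against 25, and a fold-change of 1.55 against 1.50. The lower figures belong to other reasonable readings and should not be quoted alone. No reading reaches 80%, however, so the ambiguity does not rescue the sentence.

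**The CV of 55% is the larger of two values.** This also stands. The smaller value is not given. If, as an assumption, the reference group had 55% and the comparison group 30%, raw-scale power would be about 79%. The plan chose to size on the maximum, so its sentence must be judged at 55%. Still, a reader might infer that the true chance of missing a 1.5-fold difference is 30% to 56%, and the documents do not support that. The range is conditional on a CV taken from acute dengue infection, whereas Arm III studies the response to influenza vaccine after past infection.

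**The analysis may not be a single-time t-test.** Section 12.10 plans repeated measures ANOVA for comparing groups, and Arm III is sampled on day 0, day 7 and week 3. That analysis may have different power, but the sentence in Section 12.11 is about the t-test and remains wrong for it. A reader might also infer that adjusting for day 0 would restore 80%. The gain depends on a correlation that the documents do not give, so it cannot be assumed.

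**Multiplicity over sugars.** A reader might want 0.01 divided again by three, since Section 12.11 corrects for three sugars in the first calculation. The Arm III calculation concerns afucosylated glycans only and does not say that all three sugars are tested there, so lower powers on that basis are not supported.

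**Conclusion.** The 80% power stated for Arm III is wrong on the plan's own inputs. With 25 per group, a fold-change of 1.5, a CV of 55% and a two-sided test-wise level of 0.01, power is at most about 70%, about 55% on the log scale, and about 44% with a CV of 55% in both groups on the raw scale.

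This rests on the CV applied as the plan applies it, on equal groups, and on all 25 per group being analysed. Section 12.11 restricts glycan analysis to participants with a two-fold titre rise and does not say whether Arm III is exempt. If only 20 per group were analysed (an assumption), power would be 57%, 42% or 34% for readings A, B and C.

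A reader might conclude that the multiplicity adjustment was simply forgotten. That is one possible source among several, and the documents do not show which applies. Nor do they set a rule for interpreting null results, so a specific misreading of Aim 4 is a risk rather than something the plan prescribes.

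**What to change.** In the ARM III paragraph of Section 12.11, keep n = 25 per group and the test-wise level of 0.01. State the scale on which the CV and the fold-change are defined, and the formula or software used. Then restate one of two figures to match:

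- the power for a 1.5-fold change (about 70%, 55% or 44%, according to the scale chosen), or
- the fold-change detectable with 80% power (about 1.55, 1.67 or 1.80).

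Remove the word that presents the power as guaranteed, and say that the figure assumes a CV of 55% and 25 analysed per group. The choice of scale is for the authors, because the plan does not settle it.

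The cost is protocol wording only. No extra participants are needed. The downside is a less favourable stated figure for Arm III.
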